## **1. BACKGROUND**

The development of cancer drug has been revolutionized in the last years, especially with the market authorization of targeted drugs and immunotherapy, both used alone or in combination with chemotherapy. The oncology pipeline has been enriched by 45 drugs from 2010 to 2014 for a total of 53 new indications (1). In a year, from November 2015 to October 2016, the Food and Drug Administration (FDA) approved 20 therapies for more than 12 different types of neoplasms (2). The use of supportive care therapies and growth factors has been increasing as well (1, 2). The existing anti-cancer therapies have produced a better and better clinical outcome for cancer patients, that is an increase in their 5-year overall survival for most tumours. To date, 68% of adults with cancer are alive at 5 years, compared to 50% in the 70s (1). In Italy, 5-year overall survival has been increasing when compared with the cases diagnosed in the previous three years in both men (57% in 2005-2007 vs 39% in 1990-1992) and women (63% vs 53%). This can be related to the improvement in overall survival of some of the most frequent tumours: colorectal (5-year overall survival of 64% in men and 63% in women), breast in women (87%), and prostate (91%). For some worse-prognosis tumours, the overall survival has not improved in the recent years, for example for lung tumours (14% in men and 18% in women) and pancreas tumours (7% and 9%, respectively) (3-5).

New cancer therapeutic options offer, then, better outcomes when compared with existing options and better overall survival of these patients with a low toxicity profile.

Generally speaking, cancer-related symptoms, therapy-related toxicities, and disease complications should promptly be evaluated and treated, since they negatively impact on mortality and morbidity of these patients, worsen their quality of life and increase the related costs for the National Health System. Several studies offered data on the high number of unplanned visits and/or hospital admissions due to toxicities from chemotherapy, especially about gastrointestinal issues, haematological toxicities, such as transfusion-requiring anaemia and thrombocytopenia, infections, fever and/or febrile neutropenia, but also electrolyte disorders, dyspnoea and pain (12-13).

National and international guidelines suggest the best management algorithm for the management and treatment of chemo-related toxicities, but a low adherence in everyday clinical practice can be observed, with a possible increase in the incidence and duration of adverse events, as demonstrated by several studies, especially those on the use of antiemetics (14-16, 49).

The recent development of immunotherapy has introduced a new problem related to the toxicities associated with CTLA4 and/or PD-1/PD-L1 blockade since these two pathways are involved in the regulation of the peripheral immune tolerance and are fundamental for the prevention of autoimmune problems.

To date, immune-related adverse events are graduated according to the CTCAE criteria (Common Terminology Criteria for Adverse Events) and they include a series of problems related to the immune activation, especially correlated to the activity of T lymphocytes, and they are similar to autoimmune diseases.

The most-reported toxicities are fatigue, skin problems (skin rash and pruritus), gastrointestinal problems (colitis, diarrhoea), liver issues (autoimmune hepatitis), endocrinological problems (thyroiditis, hypophysitis); less frequent the neurological issues.

However, this scenario is partially unknown and it requires the development of new tools for the evaluation of the possible consequences of these treatments, to observe the benefits in terms of overall survival, but also to evaluate the long-term effects (17-20). At the moment there are no validated predictive biomarkers that can help to identify patients at higher risk of immune-related toxicity and there is no evidence of a correlation between the toxicity development and the treatment efficacy (21).

It is fundamental that the clinician is trained about the diagnosis and the early treatment of these toxicities since an early medical intervention reduces both the severity and the duration of these problems (22).

Correct management should avail of: adequate knowledge of toxicities by the oncologists, timely information of the patients through verbal language and appropriate pamphlets, a good physician-patient communication, an appropriate application of supportive care protocols. All these elements should be included within multidisciplinary cooperation and in a standardized path including several medical professionals (medical oncologists, gastroenterologists, endocrinologist, general practitioners) with the aim of a short- and long-term evaluation of the oncological patients.

In Italy, some facilities have realized a multi-specialist dedicated team within the Oncology Units and data coming from these experiences highlight that this kind of approach determines a net reduction of unplanned hospitalizations and related costs. For such reasons in the last few years major attention has been drawn on this model, which is not focused on the cancer treatment, but on the cancer patient care (25-27).

Apart from the physicians, the involved health professionals are psychologists, spiritual assistants, and specialized nurses: some literature data show a possible positive impact on the management of toxicities through an *ad hoc* nurse intervention (28). The high specialized nurse professionals can apply an evidence-based care model, thus positively impacting the clinical outcome (29-31).

Integrated supportive care models that are proposed nowadays often deal with the most common side effects, as reported above. Still, there is a lack of randomized clinical trials that investigate the diverse supportive care modalities in the different new therapeutic settings, such as in the immunotherapy and targeted therapy setting. Such models should investigate how these new toxicities might determine a worsening of the quality of life and, then, an increase in the number of unplanned visits and hospital admissions, but also of the morbidity and the mortality.

All these things considered, major attention to the quality of life needs to have a higher offer of diagnostic and therapeutic paths with the use of one of the following modalities: either a closer hospital follow-up or the use of less invasive, home-based approaches. In the latter case, this could be performed through home visits or home phone calls. Furthermore, with major access to health information, the patient him- or herself might become a more active partner in his/her care path (1).

Specialised home assistance has been evaluated in patients undergoing oral chemotherapy. The programme consisted in home visits, 24/7 phone availability, and a weekly phone call and it has shown that the experimental group experienced a lower incidence of toxicities than the control group, but also a lower number of accesses to the reference hospital or other health facilities and a reduction of the number of days of hospital stay (28). Though positive, the results of this trial also showed increased costs. For such reasons, there are data that a phone-only nurse follow-up might be an alternative to answer to the patients'need with lower costs and thus it might determine a toxicity reduction when compared with standard monitoring (32-35).

The studies on the management of oral therapies show how fundamental it is that the involved nurses are highly specialised in the disease and trained to take immediate therapeutic decisions, such as the variation or the interruption of the treatment, through the use of pre-established and agreed protocols, that were previously shared with medical professionals (34). An educational programme on oral therapies might have the final aim of limiting the dose reductions and inadequate treatment withdrawals.

Another field of interest is the management of "acute events" that might happen between therapy cycles. Waiting for the subsequent cycle might cause a lack of reporting of some serious side event.

The vast majority of trials based on electronic monitoring evaluate the toxicities during planned visits (36-40). Only a few studies also included home control between hospital visits (through an interim phone call) (41-42). Even if data are contrasting, some data show that, by intensifying the treatment of toxicities and symptoms, the application of supportive care guidelines, as well as the training of the patient, might lead to a statistically and clinically reduction of the toxicity severity (42).

A systematic literature review on 50 studies showed that there are three types of distance interventions: treatment and side effect monitoring, but also phone-based follow up (rather than hospital follow up), and psycho-educational phone interventions (43).

In lots of studies there is a positive perception for this approach, which is not only effective and feasible, both for clinicians and patients, but also is a good way to guarantee easier access to care, especially for those patients who live far from the referral centres or in rural areas, when supportive care services are limited (42-45).

However, Liptrop revision (43) highlights contrasting results: the positive perception was reported in all three overmentioned settings, even if with higher magnitude in the field of adverse event management and treatment and in the psycho-educational settings, where phone calls are lived as an adjunct component to the standard care. The phone call is seen as an immediate source of reassurance and information, but also a continuum of care and it gives important support of emotional nature, whereas in the follow-up setting patients refer an important reassurance through physical examination and direct physician-patient relationship (43).

Another important aspect is to understand how much this method can influence medical management. Some data suggest that home management can reduce the re-hospitalization rate, since many health conditions could be treated at home, especially with good clinical surveillance (44); minor access to healthcare facilities, emergency room and general practitioners was observed (28; 34). Phone surveillance might also ease the passage from hospitalization to the outpatient setting and reduce the number of acute events (6; 45). However, further studies in this setting are needed.

NICSO trial includes the accrual of patients on adjuvant chemotherapy for breast, colon, and lung cancer, on targeted therapies or immunotherapy. It aims at evaluating the difference in terms of toxicity (but also Quality of Life, number of accesses to the emergency room, number of unplanned specialist visits, number of hospital admission and days of hospitalization) in patients who undergo a standard evaluation for prevention and treatment of toxicities compared to a group of patients who receive, apart from the standard evaluation, a periodical phone-based nurse monitoring.

To sum up, the lack of adherence to guidelines on prevention and treatment of the different toxicities induced by chemotherapy, targeted therapies, and immunotherapies is a reason for the possible increase in the incidence and duration of the same side effects.

There is a need for a precocious diagnosis of side effects in order to have better clinical management and a reduction of the intensity and duration of these events.

Better toxicity management can impact on the correct administration of cancer drugs (dose intensity).

It is still debated by the scientific community which is the best modality and evaluation tools to be used. In particular, the main questions are:

- Side effect reporting by physicians and/or patients;
- Role of nurses in the evaluation of side effects;
- The impact of the evaluation tools (frequency, executor) on the reduction of time spent with toxicity, their severity and the adherence to cancer treatment.

The recent Basch study (52) confirmed that patients that use patient-reported outcome (PRO-CTCAE) as an evaluation tool for toxicity rather than standard monitoring have a benefit in terms of overall survival. This evaluation has been conducted on a setting of metastatic patients on chemotherapy (50-52). There is then the need for randomized multicentric clinical trials in different therapeutic settings (chemotherapy, targeted therapies, immunotherapies) to evaluate the possible impact of a planned, continuative nurse monitoring of these patients.

Being proposed and sustained by the multidisciplinary NICSO (Italian Network of Supportive Care in Oncology) and having as a primary objective the improvement of toxicity management, based on the Italian law DM 17 December 2004, the study is a non-profit trial and it is a part of the health assistance in order to better the clinical practice.

## 2. OBJECTIVES

**Primary:** To evaluate the number of days patients spend with a grade 3 or higher toxicity (among those considered). The specific toxicities that are the object of evaluation are chosen among those that are clinically relevant and are more likely responsible for a reduction of treatment adherence and, then, a reduction of the benefit from such treatment.

**Secondary:**

- ✓ Incidence and duration of grade 1-2 toxicities;
- ✓ Number of emergency room accesses and unplanned specialist visits;
- ✓ Number of hospital admissions and days spent in the hospital because of treatment -related toxicities
- ✓ Evaluation of quality of life.

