## 3. STUDY DESIGN

Multicentric, randomized, open-label trial of comparison of planned, continuative nurse monitoring intervention together with an information sheet with advice about prevention and treatment of treatment-related toxicities – chemotherapy-, targeted therapy- or immunotherapy-related ones versus the exclusive use of the same information sheet.

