- c) in case of toxicities that need an urgent intervention (less than 12 hours): facilitation of the contact with the referral physician or, if the contact is not possible, suggestion to access to the hospital through the centre-specific modalities (access

to the emergency room, access to the supportive care service, and so on);

d) in case of not deferrable urgencies: direct access to the emergency room through the emergency services (118).

At the end of every phone call, the Nurse Operative Center gives a synthetic report of the detection and sends an appropriate email to the reference physicians (identified at the moment of randomisation).

During the evaluation period, according to the PRO-CTCAE (validated in Italian) (53) (Attachment 1, 2, 3), in both groups, a questionnaire for the monitoring of toxicities will be administered to each patient.

This questionnaire, which takes into consideration the previous week, monitors the frequency (F), severity (S), and intensity (I) of each symptom. A question about the number of days spent with toxicity will be performed. The administration of the questionnaire will be made through a pre-registered phone call (without an operator), which is based on an electronic score coding. This phone call does not overlap with the monitoring phone call in the specific randomisation group.

For the patients' privacy, every date coming from the project will be dealt with according to the current laws.

In each group, at the baseline visit, then every month, the EORTC QLQ-C30 questionnaire (Attachment 4) will be administered.

In both groups, there will be a monitoring activity of the number of unplanned hospital accesses (emergency room or specialist visits). An evaluation of the number of hospital admissions and days of hospital stay (due to toxicities) will be performed.

Finally, the dose intensity of the oncological drugs throughout the period of treatment will be monitored (it will be considered as the ratio between the administered dose and the planned dose). This aspect is fundamental not only for the management of the oncological therapy but also for the adherence to the recommendations of supportive care.

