### **6.2.3 Causality evaluation**

The causality evaluation by the investigator should be performed for every adverse event. The investigator's evaluation is the determination of whether there may be a reasonable possibility that the monitored pharmacological treatments may have caused or contributed to the adverse event. To give conformity of judgement, the evaluation should be defined as follows:

CAUSALITY	Description
Not related	There is no evidence in support of the drug-event relation
Improbable	The evidence that suggests a causality relation is scarce and not very sustainable (e.g. the event does not happen with a reasonable time from the drug administration). Other reasonable causes may explain the event (e.g. the patient's clinical conditions; other concomitant treatments)
Possible	There is some evidence that suggests a causal relationship (e.g. the event happens within a reasonable time from the drug administration). However, the presence of other conditions may contribute to the event (e.g. the patient's clinical conditions; other concomitant treatments)
Probable	There is evidence that suggests a causal relationship and the influence of other factors is improbable
Certain	There is evidence to support a causal relationship and the influence of other factors can be excluded
Not evaluable	There is no adequate evidence or evidence is not complete to perform a clinical evaluation of the causality relationship

All the adverse events happening during the study will be recorded in the eCRF.

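### Admissions and hospital days are tied to toxicity in sections 2 and 4 but not in section 1, and in this open-label trial attribution may differ by arm: report all-cause counts alongside

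*Protocol*

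**What the plan says.** Section 2 (Secondary) lists two measures of health-care use next to each other. The first has no cause condition: "Number of emergency room accesses and unplanned specialist visits". The second has one: it covers admissions and "days spent in the hospital because of treatment -related toxicities". Section 4 keeps the same split. Unplanned accesses are monitored without qualification, and then: "An evaluation of the number of hospital admissions and days of hospital stay (due to toxicities) will be performed".

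Section 1, where it introduces the trial, gives the aim differently. It lists admissions and days of hospitalisation with emergency and unplanned visits and restricts none of them by cause.

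On who knows what:

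- Section 3 describes a "Multicentric, randomized, open-label trial".
- Section 6.2.3 says: "The causality evaluation by the investigator should be performed for every adverse event". Section 5.2 has the centre's investigator and designated staff complete the eCRF.
- Section 3.2 randomises individual patients, and only the experimental group receives the nurse calls. Section 4 makes those calls weekly. After each one the nurse centre writes a short report and "sends an appropriate email to the reference physicians".
- The automated PRO-CTCAE call runs in both arms, but section 4 does not say that its results go to physicians.

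**The concern.** An admission is an event that either happened or did not. Whether it was due to treatment toxicity is a judgement, and section 6.2.3 grades causality on a scale that includes improbable, possible, probable and certain. When that judgement decides what is counted, the count depends on what the person judging knows and expects.

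Here the available information differs by arm. For a patient under nurse monitoring, the physician may hold a run of recent toxicity reports when the admission occurs. For a control patient there is no such run. The reports could raise attribution in the experimental arm because the toxicity is already documented. Belief in the intervention could instead lower it. Either way, the toxicity-attributed count could differ between arms with the same admissions, or agree between arms with different admissions.

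Fewer unplanned hospitalisations, with lower costs, is part of the rationale in section 1, so this endpoint will be read closely even though it is secondary.

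**Working it through.** **1. Is there a plan figure to reproduce?** Not for this endpoint: the protocol gives no admission rate, attribution share or target difference. The sample sizes in section 5.1 concern the primary endpoint. They reproduce with the two-sided, continuity-corrected two-proportion formula at alpha 0.05: 207 per arm for 15% against 5% at power 0.90, and 50 per arm for 25% against 5% at power 0.72. The total is 2 × 207 + 2 × 2 × 50 = 614, or 207 + 50 + 50 = 307 per arm. Only the 307 is used below.

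**2. The statements side by side.**

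| Place | Admissions and hospital days | Emergency and unplanned specialist visits |
|---|---|---|
| Section 1, trial aim | no cause condition | no cause condition |
| Section 2, Secondary | toxicity only | no cause condition |
| Section 4 | toxicity only | no cause condition |

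Sections 2 and 4 agree with each other; section 1 differs from both. No place describes blinded attribution or reporting both counts.

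**3. What an attribution gap could do (all rates assumed).** Recorded rate = all-cause rate × share attributed to toxicity. For simplicity this treats the outcome as the proportion of patients admitted.

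All-cause rate 20% in both arms, so the true ratio is 1.00:

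- 60% control, 80% experimental: 0.20 × 0.60 = 12%; 0.20 × 0.80 = 16%; ratio 1.33.
- 60% control, 40% experimental: 12% and 0.20 × 0.40 = 8%; ratio 0.67.
- 60% control, 70% experimental: 12% and 0.20 × 0.70 = 14%; ratio 1.17.

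**4. How often that would look significant.** With n = 307 per arm and a two-sided 0.05 test, the probability of a significant result is approximately

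Φ{ [ |p1 − p2| − 1.96 √(2p̄(1 − p̄)/n) ] / √( [p1(1 − p1) + p2(1 − p2)]/n ) }.

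For 12% against 16%, p̄ = 0.14:

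- √(2 × 0.14 × 0.86/307) = 0.0280, and 1.96 × 0.0280 = 0.0549.
- √((0.1056 + 0.1344)/307) = 0.0280.
- (0.04 − 0.0549)/0.0280 = −0.53, and Φ(−0.53) = 0.30.

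So about 30% of trials would show a difference that does not exist, against a nominal 5%. Over all-cause rates of 10%, 20% and 30%:

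| Attribution, control vs experimental | Ratio | 10% | 20% | 30% |
|---|---|---|---|---|
| 60% vs 80% | 1.33 | 16% | 30% | 45% |
| 60% vs 40% | 0.67 | 21% | 38% | 55% |
| 60% vs 70% | 1.17 | 7% | 11% | 15% |

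**5. Hiding a true effect.** With a true all-cause ratio of 0.75 and attribution of 60% against 80%, the recorded ratio is 0.75 × 0.80/0.60 = 1.00.

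**6. What the all-cause count adds.** It gives 1.00 in step 3 and 0.75 in step 5, whatever the attribution. It also gives a check by subtraction. In the first case of step 3, unattributed admissions are 20 − 12 = 8 per 100 in controls and 20 − 16 = 4 in the experimental arm. The gap of 4 mirrors the attributed gap with opposite sign, which is the pattern that reclassification would leave.

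**The case against.** Several points on the other side are sound.

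- **The attributor is not named.** A reader might infer that the unblinded treating investigator decides which admissions count. That is plausible from sections 3, 5.2 and 6.2.3 together, but section 6.2.3 is about causality of adverse events and does not mention classifying admissions. Nor does section 4 say that the physician who gets the e-mail is the person who grades causality.
- **Physicians are not divided by arm.** A reader might picture experimental-arm physicians who are informed and control-arm physicians who are not. Patients are randomised, so one physician may treat both arms. The asymmetry is that reports exist only for the monitored patients.
- **All-cause counting is not excluded.** Section 1 is unrestricted, and in sections 2 and 4 the toxicity condition could be read as qualifying only the days. The natural reading covers both, and the days are affected either way.
- **An unrestricted measure already exists.** Emergency and specialist visits need no attribution. This helps, but it does not measure admissions or length of stay.
- **A toxicity-specific endpoint suits a toxicity-management trial.** All-cause counts bring in progression-related admissions in the two metastatic groups, which have 50 patients per arm each. This is a good reason to keep the attributed count, and a reason against insisting that the all-cause count be the main comparison.
- **The analysis plan may cover it.** Attribution rules and supportive tables can be set there. But if only toxicity-attributed stays are collected, a later document cannot recover the rest.

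**Conclusion.** The point stands as a cheap improvement. Sections 2 and 4 restrict admissions and hospital days to toxicity, section 1 does not, and the protocol as written leaves a route by which attribution can differ by arm.

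The documents do not show that bias will occur, which way it would go or how large it would be. The ratios of 1.33, 0.67 and 1.17 and the false-positive rates rest on assumed admission rates and attribution shares, on pooling the three treatment groups, and on a patient-level proportion in place of a count. They show that a 20-point attribution gap would matter and that a 10-point gap would matter much less.

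An arm difference caused by the nurse algorithm sending patients to hospital is a real effect of the intervention and not part of this concern. Only the labelling of admissions is at issue. The endpoint is secondary and the primary result does not depend on it.

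**What to change.** 1. Reconcile the aim in section 1 with sections 2 and 4, so that all three say whether admissions and hospital days are all-cause, toxicity-attributed or both.
2. In sections 2 and 4, state that all-cause hospital admissions and hospital days are recorded and reported by arm beside the toxicity-attributed counts.
3. State how the two are read together: a difference in toxicity-attributed admissions or days is taken as reliable only if the all-cause count is consistent with it. An opposite shift in the unattributed remainder should be reported as a sign of possible reclassification.

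If attribution is to carry more weight, review by people who know neither the arm nor the nurse reports is an alternative that keeps the toxicity-specific endpoint, at more effort.

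**Cost.** A short edit in each section. Sections 6.2 and 6.2.3 already have all adverse events recorded in the eCRF, so part of the source data should exist. That does not guarantee admission and discharge dates for every stay: an eCRF field may be needed, or retrieval from records for group A, whose accrual is complete. The sample size is unchanged. The price in interpretation is dilution by progression-related admissions in the metastatic groups, which is why both counts should be shown.
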